3 SELECTION OF PATIENTS

3.1 Inclusion Criteria

- 3.1.1 Voluntary written informed consent before performance of any study-related procedure not part of normal medical care, with the understanding that consent may be withdrawn by the subject at any time without prejudice to future medical care.
- 3.1.2 ≥ 60 years old.
- 3.1.3 Previously untreated classical Hodgkin lymphoma (i.e., nodular sclerosis, mixed cellularity, lymphocyte depleted, lymphocyte-rich, and NOS). Nodular lymphocyte predominant Hodgkin lymphoma is not eligible.
- 3.1.4 Stage II, III, and IV disease by Ann Arbor classification.
- 3.1.5 ECOG performance status score of 0, 1, or 2.
- 3.1.6 Patients must have bi-dimensional measurable disease (as defined in section 6.1) within 60 days prior to starting treatment (at least 1.5 cm). Patients with non-measurable disease (defined in Section 6.1) in addition to measurable disease must have been assessed within 60 days prior to starting treatment.
- 3.1.7 Patients must have a bone marrow biopsy (bilateral preferred, unilateral acceptable) within 90 days prior to starting treatment.
- 3.1.8 Patients must have a MUGA or echocardiogram within 90 days prior to starting treatment and the ejection fraction must be $\geq 45\%$.
- 3.1.9 Adequate organ function including an ANC $> 1000/\text{mm}^3$, platelet count $> 75,000/\text{mm}^3$, creatinine < 2.5 mg/dl, and bilirubin < 3.0 mg/dl. Patients with documented marrow involvement by lymphoma at the time of registration are not required to meet the above hematologic parameters.
- 3.1.10 Patients must not have received prior chemotherapy or radiation therapy for the treatment of Hodgkin lymphoma.
- 3.1.11 Both females and males who have partners of childbearing potential must agree to use an effective contraceptive method during the study and for 30 days following the last dose of study drug.
- 3.1.12 Patients must sign the informed consent form before registration.

3.2 Inclusion of Women and Minorities.

- 3.2.1** Both men and women and members of all races and ethnic groups are eligible for this trial.

3.3 Exclusion criteria.

- 3.3.1** Previous treatment with SGN-35 or any other prior anti-CD30-based antibody therapy.
- 3.3.2** No currently active other (second) malignancy, other than non-melanoma skin cancers. Patients are not considered to have a “currently active” malignancy if they have completed anti-cancer therapy and are considered by their physicians to be at less than 30% risk of relapse.

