4.2.1.3 Copy of pathology report (upload to NOTIS)

4.2.1.4 Eligibility checklist (signed and dated by the treating physician – upload to NOTIS)

[figure not shown]
4.2.2 Training on eCRF completion will be provided at the time of site activation. Please refer to the eCRF demonstration videos on the CRO website for additional instructions on registering a patient. The QAM will review the registration, register the patient, assign a subject identification number, and send a confirmation of registration to study personnel. Registration will then be complete and the patient may begin study treatment.

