Patients 23 through 45 are not required to have a restaging PET or CT scan after the first 2 ‘lead in’ cycles of SGN35. PET and/or CT scans may be obtained at the investigators discretion at this time point. If there is documented progressive disease after SGN35 (i.e., prior to initiation of AVD), patients may still remain ‘on trial’ and proceed to AVD chemotherapy, however they will not receive SGN35 consolidation.

5.2.8.2 Re-staging for chemotherapy intolerant patients.

See Section 5.3.3.8 for this definition. Chemotherapy intolerant patients may proceed with consolidation SGN35 therapy if they have achieved either a PR or CR at time of chemotherapy intolerant designation. These patients should have repeat staging CT scans performed prior to initiation of SGN35 consolidation therapy (if not done within the preceding 30 days).

5.3 AVD chemotherapy.

5.3.1 Dosing.

Chemotherapy	Dose	Infusion	Timing
Doxorubicin (adriamycin)	25 mg/m ²	IV	Days 1 and 15
Vinblastine (velban)	6 mg/m ²	IV	Days 1 and 15
Dacarbazine	375 mg/m ²	IV	Days 1 and 15

(DTIC)			
--------	--	--	--

NOTE: A cycle is 28 days. Use actual weight to calculate body surface area. For further information regarding drug administration, please see Section 8.2.

5.3.2 Number of cycles.

Patients will receive 6 cycles of AVD chemotherapy, unless judged by the treating physician to be chemotherapy intolerant (see section 5.3.3.8). Each cycle is scheduled to be repeated every 28 days.

5.3.3 Dose modifications.

NOTE: All toxicities should be graded according to the CTC (version 4.0).

5.3.3.1 Hematologic Toxicity.

Dose delays and reductions of AVD chemotherapy only are to be done at the discretion of the treating physician and must be clearly documented on the Treatment eCRF in NOTIS along with the CTC (version 4.0) grade. Delays of greater than 3 weeks due to AVD toxicity must be approved by the PI and the QAM must be included on this correspondence. The following are only recommendations (are not mandatory) for modifications for AVD; SGN modifications are mandatory and are described above in Table 3. Some guidelines to be considered are for absolute neutrophil count of <500 on the day of treatment would be to consider addition of G-CSF (filgrastim) therapy. This is strongly preferred due to the long half-life of pegfilgrastim.

Patients with persistent severe neutropenia, especially despite use of granulocyte growth factor, could have reduction of doxorubicin and vinblastine by 25%.

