- 8.2.11 **Side effects.** Hematologic: Leukopenia (dose-limiting), also thrombocytopenia and anemia. Nadir 10-14 days, recovery in 21 days. Dermatologic: Alopecia, usually complete; hyperpigmentation of nail beds and dermal creases; radiation recall. Gastrointestinal: Nausea and vomiting, sometimes severe; anorexia, diarrhea; mucositis, especially with daily x 3 schedule. Cardiovascular: Arrhythmias, ECG changes; rarely sudden death. Congestive heart failure due to cardiomyopathy related to total cumulative dose; risk is greater with total doses > 550 mg/m², mediastinal irradiation pre-existing cardiac disease, advanced age; risk is reduced with weekly or continuous infusion regimens. Other: Red discoloration of urine; fever; anaphylactoid reaction; may enhance cyclophosphamide cystitis or mercaptopurine hepatotoxicity. Local effects: Vesicant if extravasated; flush along vein, facial flush.
- 8.2.12 **Nursing/patient implications.** Monitor CBC, platelet counts. Vesicant - do not extravasate. Refer to extravasation protocol if inadvertent infiltration

occurs. Advise patient of alopecia. Instruct on how to obtain wig, hairpiece, etc. Hair loss generally occurs 2-4 weeks after injection and is usually complete. Advise patient of red discoloration of urine for 24 hours after administration of the drug. Administer antiemetics as indicated. Assess for stomatitis and treat symptomatically. Generally occurs 7-10 days after injection. Be aware of "Adria" flare - most common reaction consists of an erythematous streak up the vein. It is associated with urticaria and pruritus. Occasionally the use of corticosteroids and/or antihistamines has been useful. Monitor for signs and symptoms of cardiomyopathy. Calculate total cumulative dose with each administration.

8.3 Vinblastine.

- 8.3.1 **Other names.** Velban, vinblastine sulfate, vincaleukoblastine, VLB, Velsar, Alkaban AQ.
- 8.3.2 **Classification.** Vinca alkaloid (tubulin inhibitor).
- 8.3.3 **8.3.3 Mode of Action.** Vinblastine binds to tubulin, a protein that forms microtubules, thus interfering with spindle formation during metaphase and causing cessation of cellular mitosis.
- 8.3.4 **Storage and stability.** Drug vials are stored in the refrigerator. Reconstituted vinblastine, 1 mg/ml, is stable for 30 days in the refrigerator. Further diluted to a concentration of 0.01 mg/ml in normal saline or 5% dextrose, vinblastine is stable for 24 and 72 hours, respectively, at room temperature.

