Table 4; footnote 10	The first 22 patients entered on the study will have a repeat FDG-PET	Adds the word “evaluable” that was previously omitted.	Administrative

Amendment 4 – April 16, 2013 Scientific Review Committee Approval – April 18, 2013			
Section(s) Affected	Prior Version	Amendment 4 Changes	Rationale
Table of Contents, Protocol Summary, Throughout		Formatting was changed throughout. An updated and linked Table of Contents was added. The Protocol Summary was put into a table format.	Formatting and spacing was adjusted throughout to match the new Northwestern University template.
Protocol Summary; Treatment Plan (Sections 5.1, Figure 2; 5.2.8.2 [new section added]; 5.3.2; 5.3.3.8 [new section added]); Section 7.0, Table 4 footnote 15; Section 9.3.2 Statistical Considerations, Phase II Efficacy Analysis	All 6 cycles of AVD treatment needed to be completed in order for patients to continue on the SGN-35 maintenance.	Patients who are determined to be chemotherapy intolerant may be discontinued from AVD, but may still move on the SGN-35 maintenance. Chemotherapy intolerance is now defined in section 5.3.3.8.	It has been appreciated with the initial several patients treated that there is extreme heterogeneity in this patient population including “very elderly” patients who cannot tolerate 6 cycles of chemotherapy.
Treatment Schema (section 5.1)	Indicated PET/CT was due after cycle 6 and again after consolidation.	Clarifies PET/CT is done every 3 cycles. Also clarifies PET/CT is only required for those in PR/SD. CT only is required for this in CR.	Administrative, to match the protocol parameters (Section 7.0).
Section 5.3.3 AVD chemotherapy	This section did not include dose modifications related to changes in creatinine clearance.	Section 5.3.3.6 was added, providing dose adjustments for decreasing creatinine clearance.	This was updated for safety.
Section 7.2 Pre-cycle testing.	Required all pre-study tests to be done within 4 weeks on beginning	Clarifies that the staging bone	These are not critical factors

	study treatment.	marrow and cardiac testing may be done within 3 months prior to starting treatment.	that are not likely to change within 3-4 months of study entry.

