Section 7.7 Ct scan and PET scan; Table 4	Required scans to be done within 4 weeks of starting treatment. CT of the neck was required.	Allows scans to be done within 6 weeks of starting treatment. The CT of the neck is no longer a requirement.	This is a more clinically realistic time parameter and the neck may be assessed clinically.
Section 8.1.6 (SGN-35 Preparation)	Requires drug to be diluted into at 150ml infusion bag.	Removes requirements for 150ml bag.	NMH Pharmacy does not carry 150ml infusion bags, and the size of the infusion bag does not impact the drug.
Section 8.1.7 (Required Premedication and Postmedication)	It was advised that anti-emetics are not to be given prior to the 1 st cycle.	Allows anti-nausea medications as needed.	This was done for standard clinical practice.
Amendment 5 – May 31, 2013			
Scientific Review Committee Approval – June 5, 2013			
Section(s) Affected	Prior Version	Amendment 5 Changes	Rationale
Cover Page		Adds Tufts University as a site.	An additional site is being added to aid in enrollment to the trial.
Section 1.0 (Introduction and Study Rationale)	Section 1.6.5 was not included.	Adds background on the incidence of pancreatitis seen with SGN-35. Also adds a description of the ongoing other trial of SGN-35 for elderly patients.	Additional background and safety information is now available and has been added.
Section 3.3.2	Excluded patients with a history of	Excludes patients	This protocol

(Selection of Patients)	another primary cancer that has not been in remission for at least 3 years, with exceptions indicated.	with no currently active other malignancy other than melanoma. “Currently active” is clearly defined.	includes older patients who often have a prior cancer history. This revision is for clarity.
Section 3.0 (Selection of Patients)	Section 3.3.8 did not exist.	Excludes patients with a history of pancreatitis.	This is being done for patient safety, after a severe, unexpected case of pancreatitis was seen on the study.
Section 3.2 (Exclusion Criteria)	Excludes patients with “any active systemic viral, bacterial, or fungal infection requiring IV treatment with antimicrobial therapy within 1 week prior to first dose.”	Clarifies that this must be infection requiring “ IV treatment.”	Clarification

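### No mandatory rule acts on lifetime doxorubicin dose, so a rare patient with more than 250 mg/m² from an earlier cancer can enter and pass 550 mg/m² on full AVD; a smaller point is that the LVEF stopping rule does not fix the test method

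*Combined protocol and SAP*

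**What the plan says.** **Entry.** Section 3.1.10 states: "Patients must not have received prior chemotherapy or radiation therapy for the treatment of Hodgkin lymphoma". The only other exclusion for a prior anticancer drug is for SGN-35 and other anti-CD30 antibodies (3.3.1). Under 3.3.2 a second malignancy does not count as currently active in patients "if they have completed anti-cancer therapy and are considered by their physicians to be at less than 30% risk of relapse". Admitting such patients was intended: the Amendment 5 rationale in Appendix VII says the protocol "includes older patients who often have a prior cancer history". No criterion names anthracyclines or a lifetime dose.

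**Dose.** Sections 5.3.1, 5.3.2 and 8.2.5 give doxorubicin 25 mg/m² on days 1 and 15 of six 28-day cycles. Reductions and early stopping are foreseen. For persistent severe neutropenia, 5.3.3.1 says patients "could have reduction of doxorubicin and vinblastine by 25" percent, and the Amendment 4 rationale mentions "patients who cannot tolerate 6 cycles of chemotherapy".

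**Cardiac risk.** On heart failure, 8.2.11 says the "risk is greater with total doses > 550" mg/m². It also lists mediastinal irradiation, existing cardiac disease and advanced age. Section 8.2.12 adds: "Monitor for signs and symptoms of cardiomyopathy. Calculate total cumulative dose with each administration". No section attaches a limit, reduction or stop to the calculated total.

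**LVEF.** Section 3.1.8 requires an ejection fraction of at least 45% by MUGA or echocardiogram. Section 5.3.3.5 and Table 4 (footnote 8) repeat the test, by either method, after AVD cycle 4, and allow it earlier or more often if clinically indicated. Doxorubicin stops for symptomatic arrhythmia or heart failure, for an LVEF below the institutional lower limit with an absolute fall of at least 5 points from baseline, or for any absolute fall of 15 points or more.

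**The concern.** The protocol names a cumulative dose at which heart-failure risk is greater and asks sites to keep a running total, but says nothing about what a high total should trigger. Entry looks back at prior chemotherapy only for Hodgkin lymphoma, while patients aged 60 or over with an earlier cancer are deliberately admitted. Someone who had substantial anthracycline for that cancer can therefore receive up to 300 mg/m² more doxorubicin with no mandatory check on that history.

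The written safeguards with a required action respond to cardiac function or symptoms. They detect injury rather than limit exposure. What is at stake is the safety of an occasional patient.

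The lesser point concerns the same safeguard. The LVEF rule turns on change from baseline, yet nothing asks for the repeat test to use the baseline method.

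**Working it through.** The protocol states no planned cumulative doxorubicin dose, so there is no figure of its own to reproduce.

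**Planned dose.** Inputs are 25 mg/m² per dose, 2 doses per cycle and 6 cycles (5.3.1, 5.3.2, 8.2.5).

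- Per cycle: 25 × 2 = 50 mg/m²; with a 25% cut, 37.5 mg/m².
- Six full cycles: 50 × 6 = 300 mg/m².

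**Earlier dose above which the total passes 550 mg/m²** = 550 − AVD dose received.

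| AVD received | AVD doxorubicin (mg/m²) | Threshold for earlier doxorubicin (mg/m²) |
|---|---|---|
| 6 cycles, full dose | 300 | 250 |
| 6 cycles, every dose cut 25% | 225 | 325 |
| 4 cycles, full dose | 200 | 350 |
| 3 cycles, full dose | 150 | 400 |
| 3 cycles, every dose cut 25% | 112.5 | 437.5 |

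A patient with no earlier anthracycline ends at 300 mg/m², well below 550.

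**When 550 is passed at full dose.** With earlier dose P, it is passed at the smallest k for which P + 25k > 550.

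- P just above 250: k = 12 (cycle 6).
- P just above 300: k = 10 (cycle 5).
- P = 350: k = 9, since 350 + 25 × 8 = 550 exactly (cycle 5).
- P just above 350: k = 8 (end of cycle 4).

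So with an earlier dose above 250 and up to 350 mg/m², the crossing falls in cycles 5 to 6, after the cycle 4 LVEF, which is the last routine one Table 4 shows. Above 350 it falls by the end of cycle 4.

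**LVEF rule.** For baseline B and institutional lower limit L, the fall that stops doxorubicin is the smaller of (i) a fall of at least 5 points that is also more than B − L, and (ii) 15 points. The documents do not give L, so 45 to 55 is assumed.

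| Assumed L | A 5-point fall suffices for B | A 15-point fall is needed from B |
|---|---|---|
| 45 | 45 to below 50 | 60 |
| 50 | 45 to below 55 | 65 |
| 55 | 45 to below 60 | 70 |

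For some baselines the rule turns on 5 points, so comparability of the two readings matters to it. The table shows how the rule works, not how often a change of method would alter a decision.

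**The case against.** **The safeguards are not blind to dose history.** Section 8.2.12 requires the running total, directly after the risk statement in 8.2.11, and nothing confines a clinically indicated LVEF to patients with symptoms. A physician who sees a high total has a written route to an earlier or extra test, and 5.3.3.5 stops doxorubicin on a qualifying fall. There is also a history and physical each cycle, PI discussion of other toxicities (5.3.3.7) and investigator withdrawal (10.5). This stands. A reader might infer that nothing in the plan could catch such a patient; the documents do not support that. What remains is that every response to the dose itself is optional.

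**550 mg/m² is a statement of risk, not a cap.** This also stands. A reader might infer that the plan breaches its own dose limit, but it sets none. Nor does 8.2.11 make 550 a safe endpoint in patients aged 60 or over, since it lists advanced age as a further risk factor. That is why the sponsor should confirm the limit.

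**A new exclusion cuts against Amendment 5.** It does so only slightly: other patients with an earlier cancer stay eligible. History-based exclusions are already used here, as with prior pancreatitis (3.3.8). PI discussion plus an added LVEF above a stated prior dose would be less restrictive, but would still need a written threshold.

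**The LVEF point has no shown consequence.** Correct. The documents give no difference between MUGA and echocardiogram, a site may already repeat the baseline method, and the NOTE in 5.3.3.5 lets doxorubicin resume if LVEF returns to baseline. The like-for-like PET rule in 6.6.6.2 concerns uptake time within one modality, so it is only a loose parallel. A reader might infer wrong stops or missed stops; no error rate can be derived.

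**Conclusion.** The point holds as an inexpensive patient-safety improvement for a rare case. Followed as written, the plan admits a patient with more than 250 mg/m² of earlier doxorubicin and, if all 12 AVD doses are given in full, takes that patient past the level that 8.2.11 associates with greater heart-failure risk, with no mandatory rule acting on the total. With the reductions or early stopping shown above, the threshold rises to between 325 and 437.5 mg/m².

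The number affected among 48 is not given and may be zero or very few. The content of the eligibility checklist (listed in 4.2.1.4 as "Eligibility checklist (signed and dated by the treating physician") and of the eCRFs is not shown, so nothing is claimed about what sites already record. A reader might also infer that the efficacy result is at risk; nothing in the documents supports an effect on the CR rate.

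The LVEF method point is a minor consistency matter of unknown size.

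**What to change.** (a) Add a Section 3 exclusion for prior anthracycline, given for any cancer, above a doxorubicin-equivalent of 250 mg/m², so that full AVD ends at or below 550 mg/m². The sponsor confirms the limit and the conversion for other anthracyclines. A prior dose that cannot be documented goes to the PI before registration. Record prior anthracycline dose and mediastinal radiation at baseline if the eCRFs do not already do so; the documents give no radiation threshold, so radiation is recorded only.

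(b) Minor: in 5.3.3.5 (criteria and NOTE) and Table 4 footnote 8, require the repeat LVEF to use the same method as baseline, and record the method.

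**Cost.** One eligibility line with its conversion, at most three eCRF fields, one sentence on LVEF method, and retrieval of some prior-treatment records; no extra test. A rare patient becomes ineligible, including some who would have stayed below 550 mg/m² after dose reductions, and sites lose the freedom to switch LVEF method.
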